COMIRB Protocol

COLORADO MULTIPLE INSTITUTIONAL REVIEW BOARD
[name] [contact] [contact]

Protocol #: 21-2886

Project Title: Opioid Modulation and Neural Reward Activation in Healthy Adults

Principal Investigator: [name]

Version Date: 10/28/21

I. Hypotheses and Specific Aims:

1. Evaluate whether mu-opioid receptor blockade via naltrexone alters reward activation in the ventral striatum. In a study of 10 healthy, moderate drinking adults, we will use a crossover design to examine brain activation during a functional MRI scan during placebo and mu-opioid blockade.

Hypothesis 1. Relative to the placebo scan, participants will show reduced reward-related activation in the ventral striatum during the active medication scan.

2. Evaluate whether mu-opioid receptor blockade alters threat activation in the amygdala. In the same sample and design from Aim 1, we will use the Emotion Regulation Task to assess threat related activation in the amygdala during a functional MRI scan.

Hypothesis 2. Opioid receptor modulation will not affect threat related activation, consistent with naltrexone primarily targeting reward motivation.

3. Examine whether mu-opioid receptor blockade via naltrexone alters valuation of alcohol. In the same sample and study design from Aim 1, we will use the Alcohol Purchase Task to assess subjective value of an alcoholic beverage in order to link opioid-modulation directly to alcohol motivation.

Hypothesis 3. Relative to the placebo session, participants will be willing to pay less money for an alcoholic beverage during the active medication session.

This proposal aims to fill a gap in understanding how endogenous opioid function affects reward response in the brain. One of the leading hypotheses is that individuals who drink to maximize reward are more likely to benefit from naltrexone treatment, and the current proposal would provide evidence for this in a healthy sample. Further, this work could lead to a clinical study of reward-related brain activation and response to naltrexone treatment in adults with an Alcohol Use Disorder. This stands to improve precision medicine approaches to tailor treatments for alcohol use disorder.

II. Background and Significance:

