Our goal is to better understand the neurobiology of reward processing by probing other neurotransmitter systems that interact with dopamine to regulate reward. The objective of this application is to establish whether healthy adults show reduced reward-related activation in the nucleus accumbens when ramped up to steady state dosing with naltrexone. Naltrexone is a mu-opioid antagonist and one of three medications approved by the Food and Drug Administration for the treatment of alcohol use disorder. We will also examine threat processing as a control paradigm to establish that opioid modulation primarily affects reward processing. Since diminishing reward signaling may reduce incentive to seek alcohol, we will also examine a measure of subjective alcohol evaluation. We are prepared to conduct this study based on our expertise in psychopharmacology and functional MRI studies of reward and threat processing as well as psychiatric disorders. This qualified group of investigators will make certain that our research adheres to both neuroscientific theory of reward processing as well as clinical application.

III. Preliminary Studies/Progress Report:

In a currently ongoing study, we have recruited 45 adults to complete the monetary incentive delay task and we have shown a strong main effect of cue type in nucleus accumbens activation ($F_{2,210} = 58.8, p < 0.001$), where activation is greatest during cues to gain \$5 (Figure 1).

[figure not shown]
[figure not shown]

Figure 1. Using the monetary incentive delay task, we found a main effect of cue on nucleus accumbens activation ($F_{2,210} = 58.8$, $p < 0.001$).

IV. Research Methods

A. Outcome Measure(s): There are three outcomes for this study: nucleus accumbens activation to monetary reward, amygdala activation to threat, and subjective alcohol evaluation. For nucleus accumbens activation, we will use percent signal change in response to the cue to earn \$5 during the Monetary Incentive Delay task. For the amygdala response to threat, we will use the percent signal change in response to negative images in the Emotion Regulation task. For the valuation of alcohol, we will use the Alcohol Purchase Task to assess the greatest expenditure on drinks (price paid multiplied by number of drinks).

B. Description of Population to be Enrolled:

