- b. MRI. We will conduct a Magnetic Resonance Scan. This will be completed at the Brain Imaging Center (BIC) at the University of Colorado Anschutz Medical Campus. Scanning will be conducted on a Siemens Skyra 3.0 T MR system that is equipped with high performance gradient coils (45mT/m @ 200 T/m/s), a head volume RF coil, and a 32-channel phased-array RF neurovascular coil. The system has a 70 cm bore opening and a weight capacity of 550 lbs. This will be a head-first, supine scan of the brain. Each scan will last one hour. A fMRI run sensitive to blood-oxygenation level-dependent (BOLD) contrast will be collected using T2*-weighted parameters. For anatomical reference, a high-resolution, magnetization prepared rapid gradient echo (MPRAGE) T1-weighted image will be collected during the same session.
- i. **Monetary Incentive Delay task**: The monetary incentive delay task (MID) was developed at the National Institute on Alcohol Abuse and Alcoholism (Knutson et al. 2001). The task has reliably shown that cues signaling a chance to win money recruit activation in the nucleus accumbens, and larger potential gains induce greater activity (Knutson et al. 2001). The task is comprised of three levels of monetary reward (-\$5, +\$0, +\$5). This task reliably recruits nucleus accumbens activation and has a large effect size, with a Cohen's $d > 2.0$. In the MID task, visual stimuli, such as circles, squares, and triangles, are utilized as incentive cues that code the probabilities and magnitudes of outcomes. The first box shows the cue types presented, with circles indicating the potential to win money (gain cue), triangles indicating the potential to lose money (loss cue),

and a square indicating no money will be won or lost (neutral cue). A cue is presented for 500 ms, followed by a fixation cross (2,000 to 2,500 ms) and then the target square (160 to 260 ms), during which the participant is instructed to press a button as quickly as possible to win or avoid losing money. A feedback screen (1,650 ms), in which the top number indicated the amount of money won or lost during that trial and the bottom number indicates the participant's total amount, is presented at the end of each trial.

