c. Confidentiality: Medical records will be handled to prevent breach of privacy at a level considered sufficient for sensitive health care data. Confidentiality and information technology standards will be placed to protect electronic repositories of patient data as well as other clinical patient related materials. Research data not managed electronically will be stored using codes. No personal identifiers will be used. Data will be kept in password-protected computers, either located in access-controlled areas (servers), or, if transferred onto individual workstations, on encrypted media that protect privacy even if storage media are subject to theft. Samples will be kept in locked storage in access-controlled areas. Full access to data will be provided, under conditions of confidentiality, to individuals or groups

conducting quality assurance and appropriate regulatory agencies. With these exceptions, only study investigators and their staff will have access to the samples and data. When reporting the results of this research in medical journals or at scientific meetings, the people who take part will not be named and identified. We will not release any information about subject research involvement without the subject's written permission. The Federal Privacy Act protects the confidentiality of medical records. However, the Act allows release of some information from a subject's medical record without the subject's permission; for example, if it is required by the FDA, members of Congress, law enforcement officials, or other authorized people.

d. Naltrexone:

i. Common and Serious Side Effects of Naltrexone

Nausea, sleepiness, headache, dizziness, vomiting, decreased appetite, painful joints, muscle cramps, cold symptoms, trouble sleeping, toothache.

ii. Serious side effects of naltrexone may include:

Risk of opioid overdose. Accidental overdose can happen in two ways. Naltrexone blocks the effects of opioids, such as heroin or opioid pain medicines. Patients who try to overcome this blocking effect by taking large amounts of opioids may experience serious injury, coma, or death. After receiving a dose of naltrexone, the blocking effect slowly decreases and completely goes away over time. Patients who are taking naltrexone for an OUD can become more sensitive to the effects of opioids at the dose used before, or even lower amounts. Using opioids while on naltrexone can lead to overdose and death.

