E. Potential Scientific Problems: One challenge of our study is that we will not directly observe naltrexone binding. Directly observing naltrexone's activity would require PET imaging to observe displacement of a tracer that binds to opioid receptors, but we will not do that in this study due to cost and time. Thus, even if we observe behavioral or neural effects, we will not know if naltrexone is acting at that site. However, since we are using a randomized, placebo-controlled design, we can still draw conclusions about naltrexone causing the changes even if the changes may be downstream from naltrexone's direct site of action.

F. Data Analysis Plan: Outcomes will be examined using paired t-tests for two times (active medication, placebo). Functional MRI analysis will be conducted with AFNI software (Cox 1996). Functional images will be time-slice corrected and co-registered with anatomical images. Anatomical images will be non-linearly warped to standard space and an identical transformation will be applied to the functional image. Functional images will be blurred using a 4mm Gaussian kernel and values will be scaled to have a mean intensity of 100. A regression algorithm will be applied including six regressors to account for motion. For the monetary incentive delay task, regressors of interest include the gain, loss, and neutral cue. For the emotion regulation task, regressors of interest include neutral, look, and decrease conditions. For the monetary incentive delay task, activation will be extracted from the nucleus accumbens for each of the three cues. For the emotion regulation task, activation will be extracted from the amygdala for each of the three conditions. As an exploratory analysis, we will conduct whole-brain, voxel-wise analysis.

Sample Size and Power Considerations. In terms of evaluating differences in reward activation between placebo and mu-opioid antagonism conditions, a study of mice estimated a large effect size of mu-opioid antagonism on reward response in the nucleus accumbens, with Cohen's $d > 1.0$ (Walters et al. 2005). A study of kappa-opioid receptor modulation in human reward response measured with functional MRI found a medium to large effect size of Cohen's $d = 0.6$ (Krystal et al. 2020). We specified significance level alpha=.05, two-tailed, and power of 0.8. A sample of 9 adults would provide 80% power to detect an effect size of 1.0 or greater as significant.

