G. Summarize Knowledge to be Gained: We hope to show that reward response is diminished when opioid receptors are blocked in humans. We hope to show that opioid antagonism has specificity for ventral striatal (e.g. nucleus accumbens) activation for rewards. Following this pilot, our goal is to test the effect of naltrexone in adults with an alcohol use disorder. A leading theory is that naltrexone will be more effective in patients who seek alcohol's rewarding effects compared to patients who seek relief of negative symptoms such as anxiety or withdrawal. This would help develop a precision medicine approach to treatment of alcohol use disorder, where clinicians could use reward response as a marker to determine the likelihood of naltrexone's efficacy. We would use this pilot data as part of an R01 application to fund the next study.

H. References:

Adamantidis, Antoine R., Hsing-Chen Tsai, Benjamin Boutrel, Feng Zhang, Garret D. Stuber, Evgeny A. Budygin, Clara Touriño, Antonello Bonci, Karl Deisseroth, and Luis de Lecea. 2011. "Optogenetic Interrogation of Dopaminergic Modulation of the Multiple Phases of Reward-Seeking Behavior." *The Journal of Neuroscience* 31 (30): 10829. <https://doi.org/10.1523/JNEUROSCI.2246-11.2011>.

Bechara, Antoine, Antonio R Damasio, Hanna Damasio, and Steven W Anderson. 1994. "Insensitivity to Future Consequences Following Damage to Human Prefrontal Cortex." *Cognition* 50 (1–3): 7–15.

Bernstein, David P, Laura Fink, Leonard Handelsman, and Jeffrey Foote. 1998. "Childhood Trauma Questionnaire." *Assessment of Family Violence: A Handbook for Researchers and Practitioners*.

Berridge, Kent C, and Morten L Kringelbach. 2008. "Affective Neuroscience of Pleasure: Reward in Humans and Animals." *Psychopharmacology* 199 (3): 457–80.

Brown, Sandra A, Mark G Myers, Linna Lippke, Susan F Tapert, David G Stewart, and Peter W Vik. 1998. "Psychometric Evaluation of the Customary Drinking and Drug Use Record (CDDR): A Measure of Adolescent Alcohol and Drug Involvement." *Journal of Studies on Alcohol* 59 (4): 427–38.

DeWorsop, David, Gina Creatura, Grai Bluez, Halle Thurnauer, Kimberlee Forselius-Bielen, Mohini Ranganathan, Emma Deaso, Jasra Ali Bhat, and Deepak Cyril D'Souza. 2016. "Feasibility and Success of Cell-Phone Assisted Remote Observation of Medication Adherence (CAROMA) in Clinical Trials." *Drug and Alcohol Dependence* 163: 24–30.

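### Hypothesis 1 is about reward-related activation, but the test uses the $5 gain cue alone, so a naltrexone-caused fall shared by the gain and neutral cues would be reported as reduced reward activation

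*Combined protocol and SAP*

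**What the plan says.** Section I, Hypothesis 1, predicts that "participants will show reduced reward-related activation in the ventral striatum during the active medication scan". IV.G states the conclusion sought: "We hope to show that opioid antagonism has specificity for ventral striatal (e.g. nucleus accumbens) activation for rewards".

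The outcome in IV.A is narrower: "For nucleus accumbens activation, we will use percent signal change in response to the cue to earn \$5 during the Monetary Incentive Delay task". No reference cue is subtracted.

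The task does contain a reference. IV.C.b.i describes three cue types, among them "and a square indicating no money will be won or lost (neutral cue". IV.F puts all three into the model ("For the monetary incentive delay task, regressors of interest include the gain, loss, and neutral cue") and states that "activation will be extracted from the nucleus accumbens for each of the three cues". The only test it names is: "Outcomes will be examined using paired t-tests for two times (active medication, placebo". It specifies no gain-minus-neutral contrast and no drug-by-cue test, and the exploratory whole-brain analysis names no contrast either.

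Section II presents the threat task as the control for showing that the drug acts mainly on reward. Its outcome in IV.A is amygdala signal to negative images, again with no stated subtraction of the neutral pictures.

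**The concern.** The accumbens response to a gain cue includes more than reward anticipation. It also contains whatever the region does when any shape appears and a speeded button press must be prepared. The $0 cue shares those parts without the prospect of money, so gain minus neutral is the quantity closest to the wording of Hypothesis 1.

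If naltrexone lowers the response to all cues, the gain-cue test can be significant with no change specific to reward. Blinding and counterbalancing do not protect against this, because the shift would be caused by the drug. Such a shift is possible: the side effects listed in IV.D.d.i begin "Nausea, sleepiness, headache, dizziness, vomiting". The error can also run the other way, with a general rise in cue response masking a real fall in reward response.

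At stake is the sentence the pilot is meant to support in a later grant application, namely that reward response in particular is diminished.

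**Working it through.** **Inputs from the documents.** 10 participants in a crossover (Section I, Aim 1); alpha 0.05, two-tailed; target power 0.80; design effect d = 1.0; stated sample 9 (IV.F, Sample Size and Power Considerations).

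**Inputs assumed.** The documents give neither a drug shift common to all cues nor a correlation rho between the gain-cue and neutral-cue drug differences. Both are shown as ranges. Effects are in SDs of the within-person drug difference. The gain and neutral drug differences are taken to have equal SDs.

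**Formula.** For a paired t-test with n pairs and standardised effect d, the statistic is noncentral t with n − 1 degrees of freedom and noncentrality d√n. Power is the probability that |t| exceeds the 97.5% point (2.262 for n = 10).

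**Step 1: the plan's own figure.** For d = 1.0, n = 9 gives 74.8% and n = 10 gives 80.3%. The stated 9 is one short of the exact answer of 10. The planned 10 meets the target for the gain-cue outcome.

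**Step 2: no reward-specific effect, common drop in all cues, n = 10.** The gain-cue test sees the whole drop. In gain minus neutral it cancels, so that test stays at 5%.

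| Common drop (SD) | Noncentrality | Gain cue alone rejects | Gain minus neutral rejects |
|---|---|---|---|
| 0.1 | 0.32 | 6% | 5% |
| 0.2 | 0.63 | 9% | 5% |
| 0.3 | 0.95 | 14% | 5% |
| 0.5 | 1.58 | 29% | 5% |
| 0.75 | 2.37 | 56% | 5% |
| 1.0 | 3.16 | 80% | 5% |

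These are two-sided rates. A simulation with common drops of 0.6 and 1.0 SD and rho = 0.5 gave 4.95% for the contrast.

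**Step 3: the masking case.** Take a true reward-specific fall of 1.0 SD and a common rise of 0.5 SD. The gain cue shows a net fall of 1.0 − 0.5 = 0.5 SD, so the planned test has 29% power. The contrast still sees 1.0 SD.

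**Step 4: what the contrast costs.** With equal SDs the contrast has SD √(2(1 − rho)), so a gain-specific effect of 1.0 SD becomes d = 1/√(2(1 − rho)).

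| rho | d of contrast | Power, n = 10 | n for 80% |
|---|---|---|---|
| 0 | 0.71 | 51% | 18 |
| 0.2 | 0.79 | 61% | 15 |
| 0.3 | 0.85 | 66% | 14 |
| 0.5 | 1.00 | 80% | 10 |
| 0.7 | 1.29 | 95% | 7 |

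**Step 5: proportional change.** Subtraction removes an additive shift only. Suppose the drug scales all responses by the same factor and the neutral response is half the gain response (an assumption). A 1.0 SD fall on the gain cue then comes with 0.5 SD on the neutral cue, leaving 0.5 SD. At rho = 0.5 the contrast has 29% power, against 80% for the gain cue alone.

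**The case against.** The outcome is explicit and set in advance, and the paired t-test is valid for it. The choice is partly one of estimand: the animal work cited in Section II concerns blunting of ventral striatal activity in general, so a fall across cues could be part of the mechanism, and subtraction would remove it. The plan also has its own control. The threat task shows pictures and requires button presses, so sedation or a global signal change might appear there. Finally, the size is assumed: at 0.1 to 0.2 SD the excess over 5% is small, and the contrast may lose power.

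Much of this stands. It is a reason to keep the gain-cue result and to state the cost of the contrast. It does not supply a test of reward specificity. The threat task measures another region in another task, so an unchanged amygdala response leaves open whether an accumbens change is confined to reward cues. With 10 participants a null result there is also weak evidence.

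A reader might go further and infer that a drug change in response to any cue would be reported as reduced reward activation. The documents do not support that. A change confined to the neutral or loss cue leaves the gain-cue outcome where it was, and an increase would not be called a reduction. The problem needs a decrease that includes the gain cue and is shared with the neutral cue.

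**Conclusion.** The concern holds in this form: the planned test cannot separate a reward-specific fall from a fall common to gain and neutral cues, yet Hypothesis 1 and IV.G draw the reward-specific conclusion.

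The size depends on a common shift that the documents do not give. Across 0.1 to 1.0 SD, the chance of a significant result with no reward-specific effect runs from just above nominal to the full design power. The side-effect list makes a shift plausible but gives neither a frequency nor a link to accumbens signal, so it would be wrong to infer that such a shift is expected or that the upper end of the range is likely.

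Nor does it follow that the gain-cue outcome must be discarded. Replacing it outright would be a trade-off, since the contrast matches the 80% power of the planned test only if rho is at least 0.5 under equal SDs, and does worse if the drug acts proportionally. This is a cheap improvement: it governs what may be concluded and needs no additional data.

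**What to change.** In IV.A and IV.F, pre-specify an active-versus-placebo paired t-test on accumbens percent signal change for the $5 gain cue minus the $0 neutral cue. Report it together with the gain-cue and neutral-cue drug differences. State that reduced reward-related activation is concluded only if the gain-minus-neutral result supports it, and that a similar fall in both cues is described as a general change in cue response.

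In the sample-size paragraph of IV.F, either say that the power statement applies to the gain-cue outcome or restate it for the contrast with an assumed correlation and SD ratio.

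The cost is wording in two sections and one revised power sentence. All values are already extracted, so no scans or participants are added. The price is a possibly weaker test of the reward-specific claim, which should be stated openly. Fixing the contrast in advance also prevents a choice among the three extracted cue values after unblinding.

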- a. **Recruitment, sample description and inclusion/exclusion criteria.** Participants will be recruited through advertisements on social media, paper flyering, advertising on local list-servs, and by peer recruitment. Our lab has successfully attracted over 340 participants to complete our screening measures using these methods in the past year. Interested individuals can contact the laboratory via email or phone call to arrange a phone screen, where we will assess likely eligibility for the study.
 - i. **Inclusion criteria:** A) Between 18 and 35 years of age,
 - ii. **Exclusion criteria:** A) AUDIT Score less than or equal to 14, B) Non-drinker C) positive result on urine drug screen or breathalyzer at the start of any study visit, D) inability to complete MRI (e.g. presence of ferromagnetic objects in body), E) current use of medications that alter the hemodynamic response, such as insulin, F) history of trauma resulting in loss of consciousness longer than 15 minutes, G) for females, pregnancy, H) current (within the last 3 months) use of opioids to avoid acute precipitated withdrawal due to opioid receptor antagonism I) treatment for a DSM5 disorder other than anxiety or depression through therapy J) treatment for a DSM5 disorder through medications, K) greater than 10 uses of illicit substances in the last year.
- b. **Feasibility:** We have recruited 45 participants to our laboratory's studies in the past year and conducted 45 MRI scans. To recruit ~10 participants in one year, we need to recruit 1 participant per month and conduct 2 scans per month. This is well within the capacity of our laboratory operations.

C. Study Design and Research Methods. After completing an informed consent procedure, participants will sign a consent form. They will then complete a psychiatric interview and receive 5 capsules. Participants will return five days later for visit 2. On visit 2, they will complete a medication side-effect questionnaire. If they report side effects that are more

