 - ii. **Alcohol Use Disorders Identification Test** (Saunders et al. 1993): (AUDIT) is a 10-item screening tool developed by the World Health Organization (WHO) to assess alcohol consumption, drinking behaviors, and alcohol- related problems. This study uses a self-report version of the AUDIT. Patients should be encouraged to answer the AUDIT questions in terms of standard drinks. A chart illustrating the approximate number of standard drinks in different alcohol beverages is on the questionnaire for reference. A score of 8 or more is considered to indicate hazardous or harmful alcohol use. The AUDIT has been validated across genders and in a wide range of racial/ethnic groups and is well suited for use in primary care settings.
 - iii. **Substance Use Risk Profile Scale:** (SURPS) (Woicik, Stewart et al. 2009), measures hopelessness, anxiety sensitivity, impulsivity, and sensation-seeking, and has been shown to reliably predict alcohol use.
 - iv. **Beck Depression Inventory:** (BDI) is a 21-item, self-report rating inventory that measures characteristic attitudes and symptoms of depression (Beck, et al., 1961). The BDI has been developed in different forms, including the 13-item short form and the more recent BDI-II by Beck, Steer & Brown, 1996. Internal consistency for the BDI ranges from .73 to .92 with a mean of .86. (Beck, Steer, & Garbin, 1988). Similar reliabilities have been found for the 13-item short form (Groth-Marnat, 1990). The BDI demonstrates high internal consistency, with alpha

coefficients of .86 and .81 for psychiatric and non-psychiatric populations respectively (Beck et al., 1988).

- v. **The Barratt Impulsiveness Scale:** BIS (Patton et al., 1995) is a questionnaire designed to assess the personality/behavioral construct of impulsiveness. It is the most widely cited instrument for the assessment of impulsiveness and has been used to advance our understanding of this construct and its relationship to other clinical phenomena for 50 years (for review see Stanford et al., 2009).
- vi. **Customary Drinking and Drug Use Record** (Brown et al. 1998); CDDR provides current (past 3 months) and lifetime measures of four alcohol- and other drug-related domains: level of involvement, withdrawal characteristics, psychological/behavioral dependence symptoms, and negative consequences.

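### The AUDIT exclusion runs the wrong way: as written it admits only people scoring 15 or more, which contradicts the healthy, moderate-drinking sample named in the aims

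*Combined protocol and SAP*

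**What the plan says.** Eligibility is set out in section IV.B.a. The inclusion list holds one item, age: "Inclusion criteria: A) Between 18 and 35 years of age". The exclusion list then begins "AUDIT Score less than or equal to 14, B) Non-drinker". This is the only place where an AUDIT score governs entry.

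Four other places bear on who should be enrolled:

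- Section I, Aim 1: "In a study of 10 healthy, moderate drinking adults". The project title says only that the adults are healthy; the drinking level comes from Aim 1.
- Section II, on the objective: "The objective of this application is to establish whether healthy adults show reduced reward-related activation in the nucleus accumbens".
- Section IV.C.d.ii, on the AUDIT: "A score of 8 or more is considered to indicate hazardous or harmful alcohol use".
- Section IV.G, on the next study: "Following this pilot, our goal is to test the effect of naltrexone in adults with an alcohol use disorder".

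**The concern.** An exclusion criterion removes the people who meet it. With low scores placed in the exclusion list, the rule turns away the light and moderate drinkers the study is meant to recruit and keeps those with the highest scores.

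The study population is at stake. The background in section II links psychopathology, including substance use disorders, to altered nucleus accumbens response to reward, and that response is the Aim 1 outcome. Aim 3 measures how much participants would spend on alcohol, which plausibly also depends on how much they drink. Section I says the work will give evidence in a healthy sample. A sample made up entirely of scores of 15 or more could not do that, and it may overlap with the population that section IV.G reserves for the follow-on study.

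**Working it through.** There is no planned figure to reproduce. The check is the logic of the rule, set against the protocol's own threshold.

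**Inputs**

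- Excluded: AUDIT ≤ 14 (IV.B.a, exclusion A).
- Hazardous or harmful use: AUDIT ≥ 8 (IV.C.d.ii).
- Planned sample: 10 (Aim 1).

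**Step 1: who remains.** The score is a whole number, so the complement of AUDIT ≤ 14 is AUDIT ≥ 15.

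**Step 2: distance from the protocol's own mark.** The lowest eligible score is 15. 15 − 8 = 7 points above the mark, and 15 / 8 ≈ 1.9 times it. No eligible score falls below 8.

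**Step 3: the rule as written and with its direction reversed.**

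| AUDIT score | Protocol's own description | As written | Direction reversed (exclude above 14) |
|---|---|---|---|
| 0–7 | below the hazardous-use mark | excluded | eligible, unless a non-drinker |
| 8–14 | hazardous or harmful | excluded | eligible |
| 15 or more | hazardous or harmful | eligible | excluded |

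Reversing the direction brings the range below 8 into the study and takes out 15 and above. It does not remove scores of 8 to 14, which the protocol also classes as hazardous or harmful.

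**Step 4: does anything else correct the rule?**

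- The inclusion list contains only age.
- Exclusions I and J concern people being treated for a psychiatric disorder. Someone with an untreated alcohol use disorder passes both.
- Every participant has a SCID-5 interview with a consensus diagnosis (IV.C.c), but no diagnosis is listed as a reason for exclusion.
- Section IV.D.e says that people found to have an alcohol use disorder are referred for treatment. It does not say that they leave the study.

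**Step 5: does the list itself point to a slip?** Exclusion B removes non-drinkers. It does real work if low scorers are eligible and almost none if every score of 14 or less is already out. That fits a criterion that was reversed or placed in the wrong list. The inclusion list also ends in a comma after its single item. This is weaker evidence, since it could come from text extraction, and the contradiction does not depend on it.

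**The case against.** The strongest reply is that this is an obvious slip. Aim 1 and the non-drinker exclusion make the intent plain, and staff may already screen correctly. The documents do not show how screening was done, so the effect on all 10 participants depends on the line being applied literally. That condition stands. It does not make the text safe to leave, because anyone enrolled with a score of 14 or less would meet a written exclusion and count as a protocol deviation.

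Four further points narrow the concern without removing it:

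- **Internal validity.** Each participant serves as their own control, so the comparison of naltrexone with placebo is not biased by who is enrolled. The harm is to the population the result describes. This is correct.
- **Scores of 8 to 14.** By the protocol's own mark, some hazardous drinkers are eligible in either direction, and moderate drinking is never defined by an AUDIT score. This is correct, and it is why the cut-off must be confirmed as well as the direction.
- **Background evidence.** Section II speaks of disorders, not of a given AUDIT score, and the documents give no AUDIT threshold for alcohol use disorder. Overlap with the follow-on population is therefore plausible but cannot be quantified from the documents.
- **SCID-5.** The interview would identify alcohol use disorder. But identifying it excludes nobody under the present text.

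**Conclusion.** The concern holds. As written, exclusion A admits only scores of 15 or more, all at least 7 points above the protocol's own hazardous-use mark. This contradicts the population in Aim 1 and in the stated objective, and nothing elsewhere in the document corrects it. If the rule is followed, all 10 participants are affected.

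The conclusion rests on the literal reading of the criterion and on the score being a whole number. It needs no assumption about effect size, variance or power. The damage is to the target population and to what can be concluded about healthy adults, not to the within-person treatment comparison. Eligibility text is applied directly by screeners, and no analysis can turn the wrong sample into the right one afterwards, so this must be fixed.

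**What to change.** - Reverse criterion A. Either move a score of 14 or less to the inclusion list, or reword the exclusion to cover scores above the cut-off.
- Keep the exclusion of non-drinkers, which then has a purpose.
- Have the sponsor confirm the cut-off. Aim 1, the eligibility list and the AUDIT description must be reconciled, with an explicit statement on whether scores of 8 to 14 count as moderate drinking for this study.
- State whether a SCID-5 diagnosis of alcohol use disorder affects eligibility, so that IV.C.c and IV.D.e agree with the healthy population.
- Check the wording used at the phone screen, which the document does not reproduce, and align it with the amended criterion.
- If anyone has already been enrolled, list their AUDIT scores and record which version of the rule was applied.

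The cost is a short protocol amendment, one line for the criterion itself, and any matching change to screening materials. It adds no participants or procedures.
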